### 7.4 Covariate Adjustments

It is expected that stratified randomization will lessen the need for covariate-adjusted analyses. However, in the event that adjusted analyses are necessary, a secondary comparison of the primary endpoint between groups will be made by expanding the linear mixed model to include covariates. Potential covariates include age, race, ethnicity, TENS dose/intensity, opioid use, and use of FM medications (for example, anti-depressants,  $\alpha_2$ -delta ligands). In addition, opioid use at baseline as a possible effect moderator of TENS will be examined by including an opioid\*treatment interaction in the model. If found to be significant, then secondary analyses to test for TENS effectiveness by opioid status will be performed with p-values adjusted using Bonferroni's method for multiple comparisons. Statistical significance for effectiveness of TENS+PT vs. PT alone will be based on a two-tailed test at the 0.05 significance level with treatment effect summarized as mean difference with 95% confidence interval.

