3 STUDY DESIGN

This study is a cluster-randomized, pragmatic trial conducted with approximately 450 participants across 25-35 physical therapy clinic sites from 6 health systems. We will employ a stratified randomization based on health system and size of the practice site so that half of the sites will provide TENS in addition to PT for each enrolled participant and the other half of the sites will provide routine individualized PT treatment. In the clinics randomized to standard of care, we will have specific instructions for them not to prescribe TENS to their FM patients. We recognize that some patients may be exposed to TENS through other means (relatives, friends) thus participants in the no TENS sites will also be instructed not to use TENS to prevent cross-ins; however, we believe our sample is sufficiently large to account for this potential exposure of TENS in a no TENS group. Furthermore, participants randomized to the no TENS group will receive TENS after the primary outcome data is collected at day 60 which may also prevent cross-ins and provide equipoise. At the completion of the study, we will specifically ask each participant about their TENS use, regardless of the randomization group. Primary analyses will be based on intention-to-treat.

Participants will be followed for a minimum of 60 days up to a maximum of 180 days with data collection from home at 1, 30, 60, 90, and 180 days following enrollment. The primary outcome variable will be assessed at day 60, which would be approximately at the completion of prescribed PT. Data collected from the PT clinics electronic health records (EHR) periodically

will include ICD 10 coding, the types of treatments (CPT codes), start and end dates for the episode of care, number of visits scheduled, and the number of visits attended. All patient reported measures will be obtained at home via computer, tablet, or phone.

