5.4 Prohibited Concomitant Interventions

5.4.1 Prohibited Interventions

Participants enrolled in a clinic randomized to no TENS will be asked to not use TENS therapy during the first 60 days of study participation. After the 60-day collection of the primary endpoint, participants in no TENS clinics will be given TENS units with instructions on how to use the device.

Participants will not be required to change any of their prescribed medications during the study and no specific medications will be prohibited.

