The primary endpoint to assess efficacy of TENS+PT compared to PT alone is change in movement-evoked pain during the Sit and Stand Test from baseline to 60 days. This will be tested using linear mixed model analysis for repeated measures with treatment group, time, and treatment*time interaction as fixed effects. Random effects include facilities (within treatment), and participants (within facility, within treatment). In fitting the mixed model, appropriate covariance structures for longitudinal measures within participant will be considered. Our initial approach will be to assess compound symmetry and heterogeneous compound symmetry covariance structures. However, we will also explore different covariance structures and will not only be limited to these two options. These decisions will be finalized during the UG3 phase of the proposed study. The final covariance structure will be selected based on Akaike Information Criteria (AIC) and Schwarz's Bayesian Information Criteria (BIC). From the fitted model, differences in mean change between treatment groups will be assessed by test for treatment*time interaction effect. It is expected that stratified randomization will lessen the need for covariate-adjusted analyses. However, in the event that adjusted analyses are necessary, a secondary comparison of the primary endpoint between groups will be made by expanding the linear mixed model to include covariates. Potential covariates include age, race, ethnicity, TENS dose/intensity, opioid use, and use of FM (for example, anti-depressants, α 2-delta ligands) medications. In addition, opioid use at baseline as a possible effect moderator of TENS will be examined by including an opioid*treatment*time interaction in the model. If found to be significant, then secondary analyses to test for TENS efficacy by opioid status will be performed with p-values adjusted using Bonferroni's method for multiple comparisons. Statistical significance for efficacy of TENS+PT vs. PT alone will be based on a two-tailed test at the 0.05 significance level with treatment effect summarized as mean difference with 95% confidence interval. Similar analyses will be performed for secondary outcome measures.

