10.2 Data from Quell TENS Devices

10.2.1 Collecting Data from Quell TENS Devices

Each study subject will be using two Quell devices, one designated as lower back and one designated as upper back. Designation of “Upper” and “Lower” is indicated on each unit above the Quell device serial number and is confirmed upon pairing the Quell device via Bluetooth to a smartphone application. The smartphone application will connect to Quell Health Cloud (QHC) via an account creation step, where participants enter their unique study ID (subject XXXX from site YY) into the email field as [contact]. This account creation step allows for all data on TENS usage from both devices to sync to a single Quell Health Cloud account identified by the account login credentials without personal identifiable information. The Quell TENS data (total number of minutes used per week and intensity) will be stored separately for each device by its designation/serial number. The data is stored in a segregated, secured location on NeuroMetrix servers.

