### **1.3 Interventions and Duration**

For the TENS+PT group, participants will be given TENS devices and electrodes following enrollment (signed consent) during their second PT visit. TENS will be applied to the upper and lower back with butterfly electrodes using the following parameters: mixed frequency (2-125Hz), strong but comfortable intensity, variable pulse duration from 100-250 microseconds. TENS will be applied for 2 hours per day at home when the patient is active and doing exercises and should be brought back to PT visits and used during PT treatment.

For the PT only group, participants will be given TENS units after the primary endpoint is collected at 60 days. The same parameters and instructions will be given to the participants as were given to the participants in the TENS+PT group. However, TENS instructions will be done virtually with a study team member rather than in person by their physical therapist.

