## 6. ANALYSIS POPULATIONS

### 6.1. Primary and Secondary Effectiveness Analyses (6 Month Treatment Period)

#### 6.1.1. Intent-to-Treat (ITT) Population

For the primary outcome as well as all secondary outcomes during the 6 months follow-up period, all analyses will be performed consistent with the intention-to-treat (ITT) principle – per the recent JAMA Guide to Statistics and Medicine (Detry, 2014). With treatment randomization having occurred at the practice site level, the act of signing the consent automatically assigns a participant to the treatment arm the practice site was randomized to. However, it is possible that after signing consent that an enrolled participant will not show up at the PT clinic at day 1 or will not complete the home activities at day 1 where baseline measurements are obtained.

Therefore, such a patient will be a “no-show” for the rest of the study duration. Thus, we will employ a modified ITT definition (mITT), such that the mITT population will include all participants assigned to a study arm that have completed baseline (day 1) home activities. All participants will be analyzed as-randomized, which means they will be analyzed based on the treatment to which they were randomized (whether the clinic is randomized to PT only or PT+ TENS), whether or not they remained compliant with respect to using their randomized TENS group assignment.

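### TENS dose/intensity is listed as a covariate for the secondary adjusted TENS+PT versus PT-alone comparison, where it either changes what the treatment coefficient estimates or adds nothing material

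*SAP*

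**What the plan says.** - **SAP 7.4** expects stratification to lessen the need for adjustment. If adjustment proves necessary, it expands the mixed model for a secondary between-group comparison of the primary endpoint: "Potential covariates include age, race, ethnicity, TENS dose/intensity, opioid use, and use of FM medications". The result keeps its usual reading: "Statistical significance for effectiveness of TENS+PT vs. PT alone will be based on a two-tailed test at the 0.05 significance level", with a mean difference and 95% confidence interval.
- **Protocol 9.4** repeats the list: "Potential covariates include age, race, ethnicity, TENS dose/intensity, opioid use, and use of FM" medications. Earlier in the same section, demographic and baseline variables that differ significantly between arms may be used as covariates.
- **Protocol 10.2.1** gives the source of the data: "The Quell TENS data (total number of minutes used per week and intensity) will be stored separately for each device". **SAP 1.3** makes use part of the intervention: "TENS will be applied for 2 hours per day at home when the patient is active and doing exercises".
- **Protocol 5.4.1** covers the control arm: "Participants enrolled in a clinic randomized to no TENS will be asked to not use TENS therapy during the first 60 days". PT-only participants receive units only after the Day 60 endpoint. The question on TENS use put to both arms comes at study completion (Protocol 3): "we will specifically ask each participant about their TENS use, regardless of the randomization group".
- **SAP 6.1.1** analyses participants as randomized, "whether or not they remained compliant with respect to using their randomized TENS group assignment". **SAP 7.2** defines β3 as the difference in mean change between the arms. Its primary model contains treatment, baseline pain, clinic size and a random clinic effect, with no dose term.

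Neither document says how dose would be coded for PT-only participants, or what the treatment coefficient would mean once dose is in the model.

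**The concern.** Covariate adjustment in a randomized comparison is meant to deal with imbalance in characteristics that patients bring to the trial. Age, race and ethnicity qualify. Dose does not: it is delivered treatment, recorded after TENS use starts, and by design it is absent in one arm up to the endpoint. The two arms can be compared at equal dose only at zero use, which is not the treatment the TENS arm was assigned.

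At stake is a coefficient that would be reported as the effectiveness of TENS+PT versus PT alone, with its own 0.05 test and interval, while answering a different question. Depending on how dose relates to outcome within the TENS arm, it could be attenuated, erased or inflated.

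**Working it through.** **1. The plan's own figures (SAP 9).** 342/0.76 = 450. With 13 clinics per arm, m = 171/13 = 13.15 and clinic-size CV 0.6, the design effect at ICC 0.10 is 1 + [(1 + 0.36 × 12/13) × 13.15 − 1] × 0.10 = 2.65. For a difference of 1.0 and SD 2.0, power is 81.0% (stated 81%). At ICC 0.05 it is 92.8% (stated >90%), and at 0.12 it is 76.3% (stated 78%). These figures are not in dispute; they supply the design inputs.

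**2. Algebra (SAP change-score model).** Add raw dose D with slope γ, and set D = 0 for all PT-only participants. Among controls D never varies, so γ is estimated within the TENS arm alone, and

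adjusted coefficient = total effect − γ × (mean TENS-arm dose).

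The slope γ is whatever association exists between dose and change in the TENS arm, causal or not. Protocol 9.4 uses a repeated-measures treatment-by-time model instead; there the effect depends on how dose enters.

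**3. Size of the shift.** Usage, slope and coding are assumed, because the documents give none of them. Take a total effect of −1.0 and mean use of 1 h/day.
- Slope −0.5 points per h/day: −1.0 + 0.5 = −0.5.
- Slope −1.0: −1.0 + 1.0 = 0.
- Slope +0.5: −1.0 − 0.5 = −1.5.
- Slope −0.5 with mean use 0.5 or 1.5 h/day: −0.75 or −0.25.

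**4. Standard error.** SE²(raw) = SE²(no dose) + mean² × residual variance / (171 × usage variance). At ICC 0.10 the residual variance is 4 × 0.90 = 3.6. With usage SD 0.6, 0.335² + 3.6/(171 × 0.36) = 0.1122 + 0.0585 = 0.1707, so SE = 0.413. At ICC 0.05 the SE goes from 0.285 to 0.378, and at 0.12 from 0.352 to 0.426. The increase does not depend on the slope.

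**5. Simulation.** 1,000 trials per scenario, 26 clinics, 342 completers, clinic-size CV 0.6, SD 2, ICC 0.10. TENS-arm use was drawn between 0 and 2 h/day with mean 1 and CV 0.6 (assumed). A REML random-intercept model was fitted, with a t test on 24 df. Cells show the estimate, with SE where available and the share of trials with p<0.05.

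| True effect, slope | No dose term | Raw dose | Centred on TENS-arm mean |
|---|---|---|---|
| −1.0, 0 | −0.99 (0.33, 81%) | −1.01 (0.41, 64%) | −0.99 (0.33, 81%) |
| −1.0, −0.5 | −1.01 (0.34, 83%) | −0.50 (0.42, 20%) | −1.01 (0.34, 83%) |
| 0, −0.5 | +0.01 (5%) | +0.51 (23%) | +0.01 (5%) |

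The last row has a dose slope but no net effect. That requires a within-arm association such as confounding, where heavier users differ in prognosis.

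A second simulation used equal clinics of 13 and known variance components. It gave an SE of 0.32 without dose and 0.41 with raw dose. The raw-dose coefficient was about −0.5 when half the effect acted through dose and about 0 when all of it did.

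**6. Centred coding.** With dose centred on the TENS-arm mean and PT-only at zero, the coefficient stays at the total effect. The term then does no material work in the between-arm comparison.

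**The case against.** - **The analysis may never be run.** Dose is only a potential covariate, in a secondary comparison that is itself conditional. The one selection rule stated, in Protocol 9.4, covers demographic and baseline variables, and dose is neither. This stands and lowers the likelihood of harm. It does not remove dose from the two lists, and SAP 7.4 does not repeat the rule.
- **Harm depends on unstated coding.** A treatment-plus-dose model is a legitimate exploratory model with a definable coefficient, the contrast at zero use. That is true, but SAP 7.4 reads the result as effectiveness of TENS+PT versus PT alone, which the raw-dose coefficient is not.
- **The magnitudes are assumed.** This stands. With zero slope there is no bias, only lost precision.
- **Centring need not leave the SE exactly unchanged.** With an assumed clinic-level correlation of 0.4 in use, the centred model's SE fell from 0.349 to 0.332 at slope −1.0 and from 0.371 to 0.331 at slope −1.5. At slope −0.5 it barely moved (0.337 to 0.332). So the claim is only that centring leaves the coefficient essentially unchanged.

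A reader might infer that every variable recorded after assignment should be barred. That does not follow here. Clinics are randomized before participants enrol and consent fixes the arm (SAP 6.1.1), so all participant data, including Day 1 medication use, come after assignment. The useful distinction is whether TENS treatment can affect the variable.

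A reader might also infer that the secondary outcomes are affected. SAP 8 applies the section 7 methods to them, but SAP 7.4 speaks of the primary endpoint only. Carry-over is possible, not explicit.

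**Conclusion.** The concern holds for the conditional secondary adjusted comparison and no further. Listing dose/intensity there serves no adjustment purpose. Raw coding replaces the as-randomized difference with a contrast extrapolated to zero use, and centred coding adds nothing material.

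Under the assumed usage (mean 1 h/day, CV 0.6, ICC 0.10), raw coding raises the SE from about 0.34 to 0.41, and a slope of −0.5 halves an effect of −1.0. A spurious effect when the truth is zero needs a within-arm association such as confounding. The algebra is firm for the SAP change-score model; the sizes are illustrative.

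It would be tempting to conclude that the trial's main result is compromised. The documents do not support that: the SAP 7.2 model has no dose term, so the primary test, the primary conclusion and the target of 450 are untouched. The change should still be made, because it is cheap and removes a discretionary choice that could move a reported effect.

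**What to change.** 1. Delete TENS dose/intensity from the between-arm covariate lists in SAP 7.4 and Protocol 9.4.
2. State that adjustment uses only baseline variables not affected by TENS treatment. Day 1 opioid and FM-medication use may stay.
3. Analyse dose in the dose-response analysis already named in SAP 6.1.2, reported as exploratory. Say there whether PT-only participants enter it, since the section does not. Include intensity if wanted; Protocol 3.1 already describes dose in terms that include intensity, so this may need only a clarifying phrase.
4. If a treatment-plus-dose model is kept anyway, label it exploratory, state the coding, and do not report its treatment coefficient as the effect of assignment.

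The cost is a few sentences in the two documents: no new data, and no change to the primary analysis or the sample size.

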## 8. SECONDARY ANALYSES

Analyses for secondary outcome measures will be performed using the analyses methods described in section 7 above. The list of the secondary outcomes is in section 3 above.

## 9. SAMPLE SIZE JUSTIFICATION

The required sample size was calculated to assess the effect of TENS+PT versus PT alone on the primary outcome of change from baseline to 2-month visit in pain after PT using two-independent samples t-test with inflation factor of  $[1+(m-1)*ICC]$  applied to account for average cluster size (m) and intra-cluster correlation (ICC). From the FAST study, there was a standard deviation of 2 for change in movement-evoked pain for the 5TSTS test. There was a greater decrease in pain with active- TENS compared to placebo-TENS of 1.3 (95% CI: 0.34, 2.2) for movement-evoked pain during 5TSTS. Compared to no-TENS, there was a greater decrease in pain with active-TENS of 1.8 (95% CI: 1.0, 2.8) for movement-evoked pain during 5TSTS. For this cluster randomized pragmatic trial comparing TENS+PT vs. PT alone, sample size was determined such that the statistical test at the 0.05 significance level will be able to detect a difference of at least 1.0 in mean change in pain with 80% power. Participants randomized to a treatment arm will be clustered by clinic, since PT clinics will be randomized for ease of implementation. Thus, an estimate of the intra-cluster correlation (ICC) was needed for the sample size calculation. With no prior estimate of ICC, the required sample size per treatment arm (or participants per clinic) for the desired detectable mean difference of 1.0, assuming SD=2.0, was calculated for combinations of ICC values and number of clinics per treatment arm; see Table 1 for ICC values for a sample size <300 participants per treatment arm. A pilot study examining a non-pharmacological intervention for pain by our group showed an ICC of 0.01, DeBar and colleagues used an ICC of 0.002 for sample size calculation for a chronic pain population, and Adams et al. showed widely varying ICCs between data sets, but the majority of patient-reported outcomes were below 0.095 ICC. Therefore, the study sample size was originally calculated for ICC value between 0.12 and 0.14 which resulted in a conservative sample size estimate of 456 total participants (228 per treatment arm) with complete data, for 9 to 12 clinics per arm. Table 9.1 shows the number of participants per clinic for each treatment arm, for specified ICCs and range of 9 to 12 clinics per treatment arm (C), to detect a mean difference of at least 1 (in NRS scale of 0 to 10) in pain at the 0.05 significance level with 80% power. Numbers in black are the sample size needed for combinations of ICCs and number of clinics for  $n \leq 228/\text{arm}$  while the tan numbers are for  $n > 228$  per treatment arm.

For example, if the ICC is 0.14, to reach 80% power with 12 clinics in each arm, complete data will be needed from 19 patients per clinic, 228 patients in each arm: 456 patients total. The dropout rate in the previous randomized clinical trial from our group, the FAST study, was 12% at 30-day follow-up. Since follow-up is 60 days in the proposed study, a higher drop-out rate is expected. The drop-out rate includes those patients who complete the informed consent form but do not complete the baseline assessment as a part of day 1 home activities, as well as those patients who start the study and dropout prior to day 60. To account for up to 24% drop-out rate, a total of 600 participants (300 per arm) will be enrolled. It should be noted that expected enrollment will average 25 patients per clinic for the scenario with 12 clinics per treatment arm, with some variability expected in the number of patients enrolled from each clinic. The number of patients enrolled from each clinic will be capped at 30 patients to allow for enrolling up to 20% more than originally planned.

An interim ICC recalculation will be conducted after the first 200 participants have been enrolled (approximately 1/3 of the sample) for the purpose of determining ICC for the primary outcome measure. This analysis to assess the primary outcome variable will be done for the purpose to only calculate the ICC value using the change in pain scores without regard to group assignment and will not require unblinding of randomization. Therefore, it does not have an impact on the type I error rate and there is no change in our planned analysis on our statistical analysis plan. This analysis will only be used to determine if the final number of subjects per site should be changed based on the ICC value. There are no stopping rules.

**Table 9.1:** Total study sample size with varying ICC, number of clinics per arm and subjects per clinic.

ICC	ICC values by clinics (C), per treatment arm; subjects per clinic (total subjects)			
	C=9	C=10	C=11	C=12
0.050	11 (99)	9 (90)	8 (88)	7 (84)
0.100	23 (207)	16 (160)	13 (143)	11 (132)
0.110	30 (270)	20 (200)	15 (165)	12 (144)
0.120	--	25 (250)	17 (187)	14 (168)
0.125	--	28 (280)	19 (209)	14 (168)
0.130	--	--	21 (231)	16 (192)
0.135	--	--	24 (264)	17 (204)
0.140	--	--	27 (297)	19 (228)
0.145	--	--	--	21 (252)
0.150	--	--	--	23 (276)
0.155	--	--	--	--

The original sample size calculation conservatively assumed the ICC values to change between 0.12 and 0.14, subjects to be enrolled from 12 clinics in each group, and approximately equal number of subjects to be enrolled from each clinic. During the conduct of the study, as clinics were recruited, some other clinics were deactivated. It was also observed that there was variability in the number of patients enrolled per clinic. This observed variability required the need to account for the variation in the number of enrolled participants per clinic in the sample size calculation. For this purpose, the coefficient of variation (CV), which is the ratio of standard deviation (sd) to the mean (CV = sd / mean), was used in the sample size calculation to represent variation in enrollment per clinic

The number of active clinics at the time of the ICC recalculation was 28, where 26 clinics (13 in each treatment) had at least one participant with a day 1 assessment. The observed CV was 0.6.

Plans for sample size recalculation were discussed with Drs. [name] and [name] from the NIH Collaboratory Biostatistics Core in November 2022. This meeting resulted in two recommendations: 1) recalculating the ICC value based on the adjusted model, consistent with the final analyses. 2) Calculating the ICC and the Jackknife estimate of standard error (SE) of ICC, and calculating the sample size using both the current estimate of ICC and ICC + 1SE as a conservative estimate.

These recommendations were included in the implementation of the interim ICC estimation and sample size recalculation. With 220 enrolled subjects, the estimate of the ICC based on the adjusted model, consistent with the SAP, was 0.05 with the Jackknife estimate of the SE of ICC of 0.07. Taking into account the variability in enrollment numbers per clinic (CV = 0.6) and using 13 clinics/group, the sample size was estimated at 450 enrolled subjects to obtain a final number of 342 participants completing day 60 based on a 24% dropout rate. This sample size provides >90% power for ICC = 0.05, 81% power for ICC = 0.10, and 78% power for ICC of 0.12 (ICC + 1SE = 0.05 + 0.07). The study sample was updated to 450, assuming an ICC value of 0.10. The sample size recalculation was presented to NIAMS and the DSMB. Both NIAMS and the DSMB recommended approval of the change in sample size.

